6.2.3 Follow-up Visits

- **Visit 2 Day 7 (± 2 Days):**
 - Intervention Session 1
 - Intervention Fidelity Assessment Form
 - Adverse Events
- **Visit 3 Day 14 (± 2 Days):**
 - Intervention Session 2
 - Intervention Fidelity Assessment Form
 - Adverse Events
- **Visit 4 Day 21 (± 2 Days):**
 - Intervention Session 3
 - Intervention Fidelity Assessment Form
 - Adverse Events
- **Visit 5 Day 28 (± 2 Days):**
 - Intervention Session 4
 - Intervention Fidelity Assessment Form
 - Adverse Events
- **Visit 6 Day 35 (± 2 Days):**
 - Intervention Session 5
 - Intervention Fidelity Assessment Form
 - Adverse Events
- **Visit 7 Day 42 (± 2 Days):**
 - Post-Intervention Assessment of Study Outcomes
 - Intervention Fidelity Assessment Form
 - Adverse Events

6.2.4 Completion/Final Evaluation

- **Final Visit Day 132 (± 2 Days):**
 - 3-month Post-Intervention Assessment of Study Outcomes
 - Intervention Fidelity Assessment Form
 - Adverse Events

7 SAFETY ASSESSMENTS

7.1 Adverse Events and Serious Adverse Events

The possible adverse events such as 1) reporting suicidal ideation; 2) discomfort with the PMP-I program content and/or evaluation procedures, and 3) risk of a breach of confidentiality of the collected data and/or by program personnel, and severe adverse events such as 1) suicide attempts and other events that involve hospitalization, disability, and/or death, will be reported in writing to the NIMH Program Officer according to pre-determined expectations and timeframes with the NIMH policy (<https://www.nimh.nih.gov/funding/clinical-research/nimh-reportable-events-policy.shtml>).

The PI will be responsible for the overall trial oversight in the community and safety of participants in the trial and will review all possible study-related and not-related adverse events. Field supervisors will also be responsible for describing and adhering to the procedures for identifying, monitoring, and reporting reportable events.

Adverse events: All study participants will be monitored closely daily by the field supervisors under the PI's supervision throughout the study period. Field supervisors will request study participants and their family members to immediately report any unanticipated adverse events in their family, such as 1) reporting suicidal ideation; 2) discomfort with the PMP-I program content and/or evaluation procedures, and 3) risk of a breach of confidentiality, of the collected data and/or by program personnel to field supervisor or PI directly. Field supervisors will immediately report details of such adverse events to PI. The PI will be responsible for summarizing all adverse events that are deemed expected and/or unrelated to the study in the annual progress report submitted to the UMass Amherst IRB, ISM, and NIMH Program Officer by secure email.

Serious adverse events: All study participants will be monitored closely daily by the field supervisors under the PI's supervision throughout the study period. Field supervisors will request study participants and their family members to report any unanticipated serious adverse event in their family, such as suicide attempts and other events that involve hospitalization, disability, and/or death, to the field supervisors or PI. Field supervisors will immediately report details of such adverse events to the PI. The PI will be responsible for

reporting them to the UMass Amherst IRB, ISM, and NIMH Program Officer by secure email within ten business days of the study team becoming aware of any serious adverse events.

Unanticipated problems: Field supervisors will collect completed survey questionnaires and signed informed consent from the research assistant on the same day of data collection. The PI will collect them from the field supervisor every week. In the unlikely event that the field staff loses completed survey items, the PI will be responsible for reporting this to the UMass Amherst IRB, ISM, and NIMH Program Officer by secure email within ten business days of the investigator learning of the event.

Protocol violations: The PI will strictly monitor field staffs' protocol compliance while implementing different activities, such as participant enrollment and randomization, intervention compliance, and data collection through onsite supervisions and phone conversations with field staff and participants. The PI will be responsible for summarizing protocol violations (if any) in the annual progress report that will be submitted to the UMass Amherst IRB, ISM, and NIMH Program Officer by secure email.

IRB/ISM suspensions or terminations: The PI will be responsible for reporting any suspension of IRB approval and termination of ISM to the NIMH Program Officer by secure email within three business days of receipt, including a reason(s) for the action.

All reports to the NIMH Program Officer will be made in writing by secure email and will include the following information:

- Identifying information for the research protocol (e.g., project title, investigator's name, or grant/contract number);
- The date on which the event occurred and the date of which the PI became aware of the event;
- A detailed description of the event and impact on the participant(s);
- A detailed description of the measures taken (including clinical) in response to the event (if any);

- Confirmation that the appropriate monitoring entities and regulatory bodies have been notified as needed; and
- A description of any changes to the protocol or other corrective actions that have been taken or are proposed in response to the event.

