Local community members with a high school level of education and no formal training or prior experience with mental health service providers will deliver the PMP-I. First, Drs. [name] and [name] will review with the PI the PMP-I Manual, fidelity checklists, and other training materials. Second, [name] will provide ten full days (80 hours) of intensive classroom training to community interventionists (CI) using the PMP Helpers' Training Guide. Classroom training includes information about stress and depression, the rationale for each of the strategies, necessary helping skills, extensive role-plays, peer observations, and group discussion related to core intervention concepts. Third, [name] will provide an additional two days of training in supervision to the same CIs so that they can play the

dual role of interventionists and supervisors as needed. Supervision involves discussing participants' progress and difficulties experienced when delivering strategies and role-playing on managing problems or practicing skills. Fourth, following classroom training, the PI will provide field training with at least two participants for five sessions. Finally, after overall training, we will conduct a formal evaluation of the interventionists' readiness to implement/supervise the PMP-I intervention such as using the manual, answering questions, and managing time, using a fidelity checklist, practice exercise, and role play, and will provide feedback as necessary.

[name] will provide 4 hours of breathing exercises and 16 hours of yoga practice to CIs and field supervisors using a Yoga Training Guide. Classroom training includes theoretical and practice exercises to guide participants in mind-body exercises for attention to breath, body sensation, emotional awareness, and mental function on different postures of yoga practices such as *Pranayama* (3 poses) and *Asana* (21 poses). Training will include practice assessment at the end to ensure that all staff was adequately trained, using a checklist, practice exercise, and role-plays. (Please find attached the mind-body exercise manual for the details)

Intervention Components

Psychoeducation: A brief educational session on stress management to increase awareness of the health benefits of reducing stress. To address the social isolation of many immigrants' in a new culture, we plan to educate on multi-cultural communication and social networking to promote their cross-cultural interaction.

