7.2 Independent Safety Monitor (ISM)

An Independent Safety Monitor (ISM) will be an independent member of mental health experts whose primary responsibility is to provide independent monitoring of this clinical trial in a timely fashion. We will select a member independent of any professional or financial conflict of interest (COI) with the research project and/or study investigators. A potential ISM member will provide the NIMH with his/her qualifications and a COI statement indicating that this individual has no direct involvement with the study or COI with the investigators conducting the study. The ISM will be guided by the NIMH policy governing independent data and safety monitoring boards

(<https://www.nimh.nih.gov/funding/clinical-research/policy-governing-independent-safety-monitors-and-independent-data-and-safety-monitoring-boards.shtml>).

The primary responsibilities of the ISM will be:

- Reviewing protocols, consent procedures, consent forms, and safety plans before study initiation;
- Monitoring study progress, including recruitment and retention of participants, adverse events, serious adverse events, reasons for participant withdrawal, adherence to the timeline of the study, quality of data, and protocol violations or deviations;
- Making recommendations about the continuation, modification, or termination of the trial, based on the balance of adverse events and beneficial outcomes;
- Reviewing and approving amendments to trial protocols, including consent forms.

Overall, the ISM will review enrollment data, safety data, and data integrity to maintain safety in the trial. The principal investigator (PI) will submit data reports once a year to the ISM. The data report submitted to the ISM will follow the established reporting format

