8 INTERVENTION DISCONTINUATION

This study included behavioral intervention, which does not have any noted harm. Even though subjects may withdraw voluntarily from participation in the study at any time and for any reason. Participants should continue to be followed for outcomes, with their permission, even if the study intervention is discontinued. The replacement of subjects will not be made for those who withdraw or discontinue their participation in the study. RAs will collect safety data on any subject discontinued due to adverse events or serious adverse events and will be given appropriate care under medical supervision until the symptoms of any adverse events resolve or the subject's condition becomes stable. If voluntary withdrawal occurs, the subject will be asked to continue scheduled evaluations and complete an end-of-study evaluation. In any case, every effort will be made to undertake protocol-specified safety follow-up procedures.

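### The adverse-event examples in 7.1 name discomfort with PMP-I but not with the talk programme, and include no non-serious physical event although half of PMP-I time is yoga and breathing

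*Combined protocol and SAP*

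**What the plan says.** Section 7.1 introduces non-serious events by example: "The possible adverse events such as 1) reporting suicidal ideation", then "discomfort with the PMP-I program content and/or evaluation procedures", then risk of a breach of confidentiality. The same three items return later in 7.1 as the content of the request that field supervisors make to participants and their families, who are to "immediately report any unanticipated adverse events in their family, such as" these. Serious events are described separately as "suicide attempts and other events that involve hospitalization, disability, and/or death".

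On coverage, 7.1 states that "All study participants will be monitored closely daily by the field supervisors", and the PI reviews events whether or not they are related to the study. The schedule in 6.1 and the visit lists in 6.2.3 and 6.2.4 mark adverse events without any split by arm.

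On exposure, 5.1 describes five PMP-I sessions of 180 minutes, of which 90 minutes are yoga and breathing, and five control talk sessions of 60 minutes. Community interventionists (CIs) deliver PMP-I; for the mind-body part they receive training described as "4 hours of breathing exercises and 16 hours of yoga practice to CIs" and field supervisors, with a practice assessment at the end. Section 3 states that there is no masking.

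**The concern.** When non-serious events come mainly from what people volunteer, the examples they are given influence what they mention. Here the only example about a programme names one of the two programmes. A control participant upset by a talk session can report it, but the request does not point to it. Nor does any example bring to mind a strain, a fall or a dizzy spell, which are foreseeable minor events when half the programme is physical practice. The request is also framed as one for unanticipated events, and a family might regard soreness after yoga as anticipated and leave it out.

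This matters for two uses of the data. The independent safety monitor (7.2) is to advise on the trial "based on the balance of adverse events and beneficial outcomes". And the pilot is meant to inform a larger trial (9.1), for which tolerability of the mind-body component is useful knowledge. Minor events that nobody mentions at the time cannot be reliably recovered later.

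**Working it through.** **Share of PMP-I that is physical practice** (inputs from 5.1)
- Plan's own total: 5 sessions × 180 minutes = 900 minutes. Reproduced as 5 × (90 + 90) = 900.
- Yoga and breathing: 5 × 90 = 450 minutes.
- Share: 450 / 900 = 50%.
- Control contact time: 5 × 60 = 300 minutes, so PMP-I has 900 / 300 = 3 times the contact over the same number of sessions.

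**The three non-serious examples in 7.1, by what they prompt**

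| Example | PMP-I arm | Control arm | Physical? |
|---|---|---|---|
| Suicidal ideation | yes | yes | no |
| Discomfort: programme content | yes, named | not named | no |
| Discomfort: evaluation procedures | yes | yes | no |
| Breach of confidentiality | yes | yes | no |

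The second and third rows are the two halves of one example. The asymmetry lies in a single half-item, and none of the examples is physical.

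**What else could prompt these events**
- 6.1 marks adverse events at baseline, Visits 2 to 6, Visit 7 (Day 42) and the final visit (Day 132): 1 + 5 + 1 + 1 = 8 time points, the same in both arms. Neither 6.1 nor 6.2.3 and 6.2.4 says what is asked at them.
- 7.1 contains no general definition of an adverse event, no solicited symptom list and no severity grading.
- The serious-event wording covers physical harm once it leads to hospitalization, disability or death. What remains is the non-serious physical event.
- 7.3 deals with survey distress and suicidal ideation, and also asks all participants to contact the PI with any health concerns during the intervention phase. That is neutral between arms and broad enough for a physical complaint. It is, however, an invitation to make contact rather than a question put at each visit, and it is tied to the intervention phase, whereas follow-up runs to Day 132.

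**Result.** Timing and population of capture are balanced. The stated prompts are not: programme discomfort is prompted by name in one arm, and minor physical events are prompted in neither. The documents give no expected rate of minor injury or of unprompted reporting, so the number of events that might be missed cannot be calculated.

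**The case against.** The strongest reply is that this is a matter of example wording. The list opens with *such as*, so a sprain or distress after a talk session may be reported and recorded. Daily monitoring, the visit schedule and PI review apply to every participant. Section 7.3 invites any health concern, reasons for missed sessions are recorded (5.2), and adverse effects are reviewed at weekly field meetings (7.2). The adverse-event form and the yoga manual are not in the text and may already contain neutral, physical prompts. No passage plans a formal comparison of harms or a conclusion that the programme causes no physical harm.

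Most of this stands, and it rules out several stronger readings that a reader might infer:
- *That the arms are not assessed alike.* The schedule and monitoring are common to both; only the example is one-sided.
- *That programme discomfort can be counted in one arm only.* An open list does not bar recording it in the control arm.
- *That the plan lists no physical harm.* The serious events include it.
- *That section 8 closes the question.* The sentence "This study included behavioral intervention, which does not have any noted harm" describes the intervention and is not a recording rule; the same section requires safety data on anyone discontinued for adverse events.

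What the reply does not remove is the difference between permitting a report and prompting one. The text shows no fixed set of questions, and the one request whose content is spelled out is the one that is uneven.

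**Conclusion.** The point holds as a moderate reporting gap. The examples that shape non-serious reporting name discomfort with one programme and no minor physical event, while 50% of PMP-I time is yoga and breathing. Because participants and staff know the allocation, and capture rests largely on participant and family reports, a difference in programme discomfort between arms could partly reflect the wording of the request. A low count of minor injuries could likewise reflect the absence of a question. The threefold difference in contact time is a separate reason for care with any raw comparison.

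The conclusion rests on two assumptions: that examples influence what people volunteer, and that the unseen adverse-event form does not already ask the same neutral questions, including about physical symptoms. If it does, only a cross-reference is missing. The efficacy analysis is not touched. The change is worth making because it is cheap, not because the plan would otherwise fail.

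**What to change.** In 7.1, at both places where the list appears:
1. Change item 2 to *discomfort with the content of the assigned programme (PMP-I or talk) and/or evaluation procedures*.
2. Add an item: *physical injury or symptom during or after a session or home practice*.
3. State that the same questions are put to both arms at each visit where 6.1 already schedules adverse events.

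If the adverse-event form already does this, 7.1 should cite it instead.

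The cost is a few lines of text and, if needed, an edit to the form. No visit or staff is added. The downside is more minor events to record and summarise. The change concerns only what is asked and recorded; how any event is handled stays as the protocol sets out.

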7.2 Independent Safety Monitor (ISM)

An Independent Safety Monitor (ISM) will be an independent member of mental health experts whose primary responsibility is to provide independent monitoring of this clinical trial in a timely fashion. We will select a member independent of any professional or financial conflict of interest (COI) with the research project and/or study investigators. A potential ISM member will provide the NIMH with his/her qualifications and a COI statement indicating that this individual has no direct involvement with the study or COI with the investigators conducting the study. The ISM will be guided by the NIMH policy governing independent data and safety monitoring boards

(<https://www.nimh.nih.gov/funding/clinical-research/policy-governing-independent-safety-monitors-and-independent-data-and-safety-monitoring-boards.shtml>).

The primary responsibilities of the ISM will be:

- Reviewing protocols, consent procedures, consent forms, and safety plans before study initiation;
- Monitoring study progress, including recruitment and retention of participants, adverse events, serious adverse events, reasons for participant withdrawal, adherence to the timeline of the study, quality of data, and protocol violations or deviations;
- Making recommendations about the continuation, modification, or termination of the trial, based on the balance of adverse events and beneficial outcomes;
- Reviewing and approving amendments to trial protocols, including consent forms.

Overall, the ISM will review enrollment data, safety data, and data integrity to maintain safety in the trial. The principal investigator (PI) will submit data reports once a year to the ISM. The data report submitted to the ISM will follow the established reporting format

developed in consultation with NIMH. The report will include the key variables necessary for monitoring the safety and quality of data collection and the integrity of the study, including inclusion criteria, informed consent, subject enrollment and retention, data confidentiality, intervention compliance, dropouts, adverse events, protocol compliance, data quality, and baseline characteristics of study participants. The ISM will have access to all safety and data quality information collected and have the authority to stop the study if it is determined that there are unacceptable risks to participants. The ISM will also review the study protocol, informed consent, and all relevant documents before the study's onset and review and approve amendments to these documents. The ISM will issue a monitoring report to the PI following each review. The PI will submit all review reports to the UMass Amherst IRB and NIMH Program Officer in annual progress reports.

The PI will be responsible for monitoring procedures during the study, including enrollment, data and sample collection, and participant safety and well-being. During the trial, experienced field supervisors from the Bhutanese community, who are trained as a community health worker and have worked with the PI in previous church and family-based mental health intervention studies with depressive and suicidal ideation outcomes, will take responsibility for the day-to-day oversight of the participants and field teams in the implementation of the trial. Field supervisors will immediately report any noted adverse events among participants, such as suicidal ideation, to the PI. The PI will report adverse events data to the ISM, UMass Amherst IRB, and NIMH Program Officer following NIMH guidelines for reportable events, as described below (<https://www.nimh.nih.gov/funding/clinical-research/nimh-reportable-events-policy.shtml>).

To monitor trial protocol compliance and participants' safety, the PI will visit the trial site once every two weeks or more if needed. The PI will also conduct a weekly meeting with field staff (in-person and online on a rolling basis) to perform the continuous review of data and participant safety. The PI will be available for discussions by telephone and via email for participants and field staff if needed at any time. The PI will review the adverse effects and responses of the trial at these meetings. With this trial monitoring plan, the PI will oversee the participant safety protocols and the timely follow-up of any adverse events or serious adverse events throughout the study, as well as the reporting of adverse events to the ISM. The overall purpose of the day-to-day supervision and field visits, and any

independent monitoring visits, will be to verify that: the well-being of trial participants is protected; reported trial data are accurate and complete, and the conduct of the trial complies with the approved protocol and amendments.

7.3 Potential Risks and Mitigation Strategies

We do not anticipate any significant risks due to participation in research-related activities, based on our previous pilot intervention experience with similar mental health outcomes in the same population.

First, RA will remind each participant that if they perceive any question to be too personal, they can choose not to respond. Participants may feel hesitant to answer some of the questions regarding depression and suicidal ideation. In such cases, participants are free to skip such questions or are free to withdraw from participating in the study overall. If participants feel upset during or after completing the survey or find that some questions or aspects of the study triggered distress, the RA will immediately contact the PI. The PI will then immediately assist participants (in their native Nepali language) and help them to connect with mental health support services in coordination with the field supervisor. The RA will also provide them with contact information for emergency and other mental health support available locally but independent of the study.

Second, the field-team will be trained to recognize potential risks that require immediate reporting, such as suicidal ideation. If any participants respond “yes” to a questionnaire item that measures suicidal ideation or develops suicidal ideation during the intervention implementation phase, the RA will immediately contact the PI. The PI will then immediately assist participants (in their native Nepali language) and help them connect to mental health support services available in the area in coordination with the field supervisor. The field supervisor will provide the necessary support to them for setting up their appointment with primary health care providers if needed. The field supervisor will also make a follow-up home visit to monitor their mental health condition, as necessary.

Finally, all participants will be asked to contact the PI directly if they have any health concerns and/or need help during the intervention implementation phase. We would like to identify field supervisors as an alternative contact person for participants and research assistants if the Principal Investigator (PI) is busy or unavailable, for whatever reason

needed. We plan to recruit two field supervisors from the Bhutanese community. Both are trained as community health workers and have extensive experience in providing various health services (including referral for mental health problems), as they are part-time employees of local level non-profit organizations (e.g., Ascentria Care Alliance) and the MA Department of Public Health. Both of them have worked with the PI in previous church and family-based mental health intervention studies with depressive and suicidal ideation outcomes. They are familiar with available mental health support services available in the community and have been providing care and support to the community members in a mental health crisis, bearing the dual responsibility of community leader and church pastor. Field supervisors will make regular follow-up visits to monitor participants' mental health conditions. A pamphlet will be provided to participants who need additional help, which describes the community's psychological services. We handled such cases successfully when we conducted our previous three studies, all of which included needs assessments, church-based and family-based mental health promotion interventions, measured suicidal ideation and depressive symptoms, and utilized our well-established networks in the clinical and community settings.

